#### **14.3.4 Analysis of primary endpoint**

The efficacy of delgocitinib cream compared with vehicle will be analysed in a within-subject comparison of lesion-specific treatment success (defined as an IGA score of 0 or 1 at Week 6) using McNemar's test.

The PP analysis set will be the primary analysis set for the primary endpoint. The analysis will be repeated on the FAS as a sensitivity analysis.

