| Investigational medicinal products | 
 
• Name of IMP: delgocitinib cream.
 
• Active substance: delgocitinib.
 
• Formulation: cream.
 
• Formulation strength: 20 mg/g and vehicle.
 
• Dose and method of administration: topical application twice daily.
 
   |

|  |   |
|--|---|
| Duration of treatment                  | 6 weeks.  |
| Number of subjects                     | This trial aims to have 36 subjects evaluable for the primary endpoint. Assuming a drop-out rate of 20%, approximately 45 subjects will be randomised to achieve this.  |
| Number and distribution of trial sites | Approximately 20 sites in several countries in the EU and/or United States.   |
| Statistical methods                    | 
Primary endpoint:
 
The efficacy of delgocitinib cream compared with vehicle will be analysed in a within-subject comparison of lesion-specific treatment success (defined as an IGA score of 0 or 1 at Week 6) using McNemar's test.
 
Secondary endpoints:
 
Within-subject comparisons of the numbers of AEs, subjects with AEs, and treatment-related, lesion-specific AEs will be done by treatment using a Wilcoxon signed rank test.
 
Within-subject comparisons of lesion-specific binary endpoints to assess treatment difference at Week 6 will be done by McNemar's test.
 
Within-subject comparisons of lesion-specific disease activity scores to assess treatment difference at Week 6 will be done by a Wilcoxon signed rank test.
 
The analysis of the primary and secondary endpoints will be performed on the per protocol analysis set and repeated for the full analysis set as a sensitivity analysis.
 |
| Signatory investigator                 | [name], Univ. [name]. Med.
Department of Dermatology, Venereology and Allergology, Campus Charité Mitte, Berlin, Germany  |
| Sponsor                                | LEO Pharma A/S, [name].   |

[figure not shown]

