### 14.2 Trial analysis sets

All subjects screened in the trial will be accounted for in the CTR.

All randomised subjects will be included in the full analysis set (FAS). Exclusions from the FAS can be considered in special cases as described in ICH E9, Section 5.2.1 (Full Analysis Set). If it is decided to exclude a randomised subject from the FAS, a justification addressing ICH E9 will be given.

A per protocol (PP) analysis set will be defined by excluding subjects from the FAS who fulfil any of the following criteria:

- Receive no treatment with the IMPs.
- Do not complete the trial up to and including the Week 6 visit.
- Fail to provide efficacy data at the Week 6 visit.
- Are known to have used the wrong IMP on 1 or both target lesions.
- Do not fulfil the disease-defining inclusion criteria (that is, inclusion criteria no. 3-6).

Further exclusion of subjects or subject data will be decided upon after a blind review of the data, reviewing all the remaining in- and exclusion criteria, but focusing on concomitant medication that may affect DLE and also considering compliance and violations of visit windows.

A safety analysis set will be defined as all subjects who received IMP.

The decisions regarding inclusion/exclusion of subjects or subject data from the trial analysis sets will be documented in the analysis set definition document before breaking the randomisation code.

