#### **14.3.5 Analysis of secondary endpoints**

Within-subject comparisons of the numbers of lesion-specific, treatment-related AEs will be done by treatment using a Wilcoxon signed rank test.

Within-subject comparisons of lesion-specific binary endpoints ( $\geq 2$ -point reduction in erythema score, and  $\geq 2$ -point reduction in IGA score from baseline to Week 6) to assess treatment difference will be done by McNemar's test.

Within-subject comparison of lesion-specific erythema score and total skin disease activity score to assess treatment difference at Week 6 will be done by a Wilcoxon signed rank test.

The PP analysis set will be the primary analysis set for the secondary endpoints. The analysis will be repeated for the FAS as a sensitivity analysis.

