### **14.3.9 Analysis of safety**

The analysis of safety will be based on the safety analysis set.

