#### **14.3.11 General principles**

All significance tests will be 2-sided using the 5% significance level. All tests will be interpreted exclusively in a descriptive manner, i.e. independently of other tests. All confidence intervals will be presented with 95% degree of confidence, unless otherwise specified.

An observed-cases approach will be used for tabulations of data by visit (that is, involving only those subjects who attended each specific visit).

Categorical data will be summarised using the number and percentage of subjects in each category. Lesion-specific categorical data will be summarised by cross-tabulation within subject by treatment. Continuous data will be summarised using the mean, median, SD, and minimum and maximum values.

All the analyses specified in the protocol will be reviewed in relation to the blinded data actually obtained, and the statistical analysis plan will be finalised before breaking the randomisation code.

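### The per-protocol set is primary for the primary and secondary endpoints, with the FAS only a sensitivity analysis; for the lesion-specific related-AE comparison this conflicts with the safety-set rule

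*Combined protocol and SAP*

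**What the plan says.** Section 14.3.4: "The PP analysis set will be the primary analysis set for the primary endpoint". Section 14.3.5: "The PP analysis set will be the primary analysis set for the secondary endpoints". The synopsis agrees: "The analysis of the primary and secondary endpoints will be performed on the per protocol analysis set". In each place the FAS, defined as all randomised subjects, is a repeat for sensitivity.

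Section 14.2 lists the grounds for leaving PP. One concerns baseline status (inclusion criteria 3 to 6). The others arise after randomisation: no treatment received, no Week 6 efficacy data, known use of the wrong product on a lesion, and this one: "Do not complete the trial up to and including the Week 6 visit". The list stays open: "Further exclusion of subjects or subject data will be decided upon after a blind review of the data", with attention to concomitant medication, compliance and visit windows.

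Subjects who stop treatment before Week 6 are asked to attend a primary endpoint visit six weeks after first application (Section 4, footnote d; Section 10.3). Panel 2 schedules IGA there.

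On adverse events, Section 14.3.5 begins: "Within-subject comparisons of the numbers of lesion-specific, treatment-related AEs will be done by treatment using a Wilcoxon signed rank test". Its closing rule on analysis sets covers that test as well. Section 14.3.9 says: "The analysis of safety will be based on the safety analysis set".

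**The concern.** Lack of efficacy and adverse events are both listed reasons for stopping treatment or leaving the trial (Section 10.1). Unacceptable worsening of the disease is a ground for discontinuing treatment (Section 10.2.1). Membership of PP can therefore depend on how a lesion responded. The headline rates then describe subjects who stayed on protocol rather than those randomised, and the set that could use the Week 6 IGA of discontinuers is ranked second.

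For the AE comparison, a subject who leaves before Week 6 because of a treatment-related reaction on a target lesion falls outside the primary analysis of that same endpoint.

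**Working it through.** **1. The plan's own figures.** Section 14.1 gives 36 completers, 20% drop-out, and success of 5% on vehicle and 35% on delgocitinib, tested at 5% (two-sided by Section 14.3.11).
- Randomised: 36/(1 − 0.20) = 45, as stated, so 9 drop-outs are assumed.
- Wald power with independent lesions: variance (0.05×0.95 + 0.35×0.65)/36 = 0.275/36, standard error 0.0874. Φ(0.30/0.0874 − 1.96) = 93.0%, consistent with the stated minimum of 90%.
- The within-subject correlation is not given. As the probability that both lesions respond runs from 0% to 5%, this power runs from 89.8% to 97.5%.

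**2. PP against FAS.** Assumptions: the 36 PP subjects respond at the planned rates, and k of the 9 drop-outs stopped treatment, gave a Week 6 IGA and are outside PP. The protocol gives no value for k.
- If all k fail on both lesions, the FAS rates are 0.35×36/(36+k) and 0.05×36/(36+k).
- If the k respond at 35% on delgocitinib and 0% on vehicle, the rates are 35% and 0.05×36/(36+k).

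| k | Fail on both: rates | Difference | 35% v 0%: difference |
|---|---|---|---|
| 0 | 35.0% v 5.0% | 30.0 | 30.0 |
| 3 | 32.3% v 4.6% | 27.7 | 30.4 |
| 6 | 30.0% v 4.3% | 25.7 | 30.7 |
| 9 | 28.0% v 4.0% | 24.0 | 31.0 |

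If these subjects belong to PP, they cause no shift. The table illustrates and does not bound the effect. It leaves out other PP exclusions, such as wrong product or blind-review decisions.

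**3. Effect on the test.** Exclusion removes both lesions of a subject, so every retained pair still has one lesion per treatment. Pairs that fail on both lesions are concordant and do not enter McNemar's statistic, so adding them lowers the rates and leaves p unchanged.

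**4. Power with the FAS primary.** Exact McNemar, independent lesions:
- 36 pairs at 35% v 5%: 86.8%.
- 45 pairs at 28% v 4% (rates multiplied by 0.8, the drop-outs counting as failures on both lesions): 86.4%.
- 45 pairs at unchanged rates (all 9 retrieved): 94.4%.

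Across the possible range of joint response, the first figure runs from 81.3% to 97.8% and the second from 81.0% to 97.5%. The FAS therefore costs at most a fraction of a point in these cases.

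**5. The AE endpoint.** Panel 3 lists lesion-specific, treatment-related AEs as a secondary endpoint. Section 14.3.5 and the synopsis put secondary endpoints on PP, which requires completion to Week 6. Section 14.3.9 puts safety on everyone who received treatment. Both rules cover the signed-rank comparison and they name different sets. Section 14.3.9.1 plans other lesion-level related-AE analyses on the safety set, including a McNemar comparison, but not this count test.

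**The case against.** This is an exploratory phase 2a trial, sized on subjects who complete according to the protocol, so a PP primary analysis matches the sizing. The FAS repeat is prespecified, set decisions are recorded before unblinding, and Section 14.3.11 says: "All tests will be interpreted exclusively in a descriptive manner, i.e. independently of other tests". Both results will be available. All of this stands and limits the consequence. It does not remove the point, because in a descriptive trial the estimated rates are the main output, and those are what the analysis set changes.

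The PP-versus-FAS shift also depends on an open reading. Section 10.1 separates stopping treatment from leaving the trial, and Section 10.3 labels the retrieval visit as Week 6. A discontinuer who attends could therefore count as completing to Week 6 and stay in PP. That reading is possible, and so is the opposite one. The text needs to say which applies.

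On AEs, Section 14.3.9.1 already compares lesions with related AEs on the safety set, and the FAS repeat of the signed-rank test keeps early leavers. This also stands. What is left is a conflict over which set governs one named secondary analysis.

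A reader might go further and infer three things that the documents do not support:
- **That PP biases the trial towards delgocitinib or undermines the test.** Pairs stay intact, and the illustrations move the difference both ways.
- **That the FAS analysis as planned uses the retrieved IGA.** The visit makes this possible, but no section says so.
- **That missing Week 6 data threaten the result.** Nothing is imputed, but counting missing pairs as failures on both lesions leaves McNemar's p unchanged, and the SAP remains open until unblinding.

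**Conclusion.** The point holds in two parts.

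First, PP is primary although it excludes randomised subjects for later and possibly outcome-related events. The FAS, which could use the Week 6 IGA of treatment discontinuers, is secondary, and the PP status of those discontinuers is unstated. The exposure is to the population described and the headline rates. In the illustrations the difference lies between 24 and 31 points against 30 in PP, and does not move if these subjects belong to PP. This rests on the planned 35% v 5%, the 9 assumed drop-outs and an unknown number retrieved.

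Second, Section 14.3.5 and the synopsis conflict with Section 14.3.9 on the analysis set for the lesion-specific, treatment-related AE comparison. The PP choice can drop subjects who left because of such an event. Other safety-set analyses and the FAS repeat limit the damage.

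Both should be corrected before unblinding. Neither invalidates the design.

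**What to change.** Before unblinding, in Sections 14.2, 14.3.4, 14.3.5 and the synopsis:
1. Make the FAS primary for the primary and secondary efficacy endpoints. For IGA endpoints, use each lesion's Week 6 score from Visit 5 or the primary endpoint visit, regardless of treatment discontinuation. Keep PP as supportive, and state whether primary endpoint visit attendees belong to it.
2. Reconcile Section 14.3.5 and the synopsis with Section 14.3.9 so that the lesion-specific, treatment-related AE comparison uses the safety analysis set.

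The cost is a few sentences, a possibly slightly less favourable headline rate, and almost no power (exact McNemar 86.4% v 86.8% in the fail-on-both case).

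Two additions are optional and separate from the point. One is a missing-data sensitivity analysis; to inform the test it would have to assign discordant outcomes to missing pairs. The other is skin lesion activity scoring at the primary endpoint visit, where Panel 2 leaves that cell blank. It would need a protocol amendment and could not recover visits already held.

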#### **14.3.5 Analysis of secondary endpoints**

Within-subject comparisons of the numbers of lesion-specific, treatment-related AEs will be done by treatment using a Wilcoxon signed rank test.

Within-subject comparisons of lesion-specific binary endpoints ( $\geq 2$ -point reduction in erythema score, and  $\geq 2$ -point reduction in IGA score from baseline to Week 6) to assess treatment difference will be done by McNemar's test.

Within-subject comparison of lesion-specific erythema score and total skin disease activity score to assess treatment difference at Week 6 will be done by a Wilcoxon signed rank test.

The PP analysis set will be the primary analysis set for the secondary endpoints. The analysis will be repeated for the FAS as a sensitivity analysis.

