## 6 Trial objectives and endpoints

### Panel 3: Objectives and endpoints

| Objectives   | Endpoints   |
|--|---|
| Primary objective   | Primary endpoint   |
| To investigate the efficacy of delgocitinib cream 20 mg/g twice daily on active DLE target lesions.  | 
 
Target lesions with Investigator's Global Assessment (IGA)a score of 0 or 1 at Week 6.
 
   |
| Secondary objectives  | Secondary endpoints  |
| 
To evaluate the safety of delgocitinib cream 20 mg/g twice daily on active DLE target lesions.
 
To further investigate the efficacy of delgocitinib cream 20 mg/g twice daily on active DLE target lesions.
 | 
 
Adverse events (number of AEs and number of subjects with AEs) up to Week 6.
 
Number of lesion-specific, treatment-related AEs up to Week 6.
 
A <math>\geq 2</math>-point reduction in IGA score at Week 6 compared to baseline.
 
A <math>\geq 2</math>-point reduction in erythema scoreb at Week 6 compared to baseline.
 
Erythema score at Week 6.
 
Total skin disease activity score (sum of scores for erythema, scaling/hyperkeratosis, and oedema/infiltration)b at Week 6.
 
  |
| Exploratory objectives  | Exploratory endpoints  |
| To further investigate the efficacy of delgocitinib cream 20 mg/g twice daily on DLE target lesions with active disease.   | 
 
IGA score at Weeks 2, 4, and 6.
 
Patient's Global Assessment (PaGA)c score of 0 or 1 at Week 6.
 
A <math>\geq 2</math>-point reduction in PaGA score at Week 6 compared to baseline.
 
PaGA score at Week 6.
 
Scaling/hyperkeratosis scoreb at Week 6.
 
Oedema/infiltration scoreb at Week 6.
 
Dyspigmentation scoreb at Week 6.
 
Scarring/atrophy scoreb at Week 6.
 
Total skin disease damage score (sum of scores for dyspigmentation and scarring/atrophy)b at Week 6.
 
Total skin lesion disease score (sum of scores for total skin disease activity and total skin disease damage)b at Week 6.
 
 |

| Objectives  | Endpoints  |
|---|--|

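### The per-protocol set is named as primary for the secondary adverse-event endpoints, and the synopsis plans by-treatment AE tests that cannot be formed for events away from the target lesions

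*Combined protocol and SAP*

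**What the plan says.** Panel 3 (section 6) places two AE endpoints among the secondary endpoints: "Adverse events (number of AEs and number of subjects with AEs) up to Week 6" and "Number of lesion-specific, treatment-related AEs up to Week 6".

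Section 14.3.5 contains one AE test, a Wilcoxon signed rank comparison of the related lesion-specific counts. It closes with "The PP analysis set will be the primary analysis set for the secondary endpoints", adding a repeat on the FAS as a sensitivity analysis. The Statistical methods entry of the synopsis is broader: "The analysis of the primary and secondary endpoints will be performed on the per protocol analysis set", again with an FAS repeat. The same entry announces by-treatment signed rank tests for three quantities, beginning "Within-subject comparisons of the numbers of AEs, subjects with AEs" and ending with the related lesion-specific AEs.

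Section 14.3.9 says "The analysis of safety will be based on the safety analysis set". Section 14.2 defines that set as everyone who received trial product. It forms PP by removing from the FAS, among others, subjects who "Do not complete the trial up to and including the Week 6 visit" and those who "Are known to have used the wrong IMP on 1 or both target lesions".

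**The concern.** An AE endpoint should normally be read on everyone exposed. Under the PP rule, membership of the set labelled primary depends partly on staying to Week 6, and an AE can be the reason a subject does not stay. The plan does not say whether section 14.3.5 or section 14.3.9 governs the AE endpoints. A report that follows the labels would lead with the PP result for a named safety endpoint.

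The synopsis raises a second problem. A signed rank test by treatment needs a delgocitinib value and a vehicle value within each subject. For AEs in general, the design does not supply that pair.

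**Working it through.** The plan attaches no figure to this point, so the check is a comparison of the text.

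**1. Where each AE quantity is analysed, and on which set**

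| Place | Quantity | Method | Set |
|---|---|---|---|
| Synopsis | Number of AEs; subjects with AEs; related lesion-specific AEs | Signed rank test by treatment | PP, repeated on FAS |
| 14.3.5 | Related lesion-specific AE counts | Signed rank test by treatment | PP, repeated on FAS |
| 14.3.9.1 | AEs and subjects with AEs | Tabulated, no treatment split | Safety set |
| 14.3.9.1 | Lesions with lesion-specific AEs, overall and related | McNemar's test | Safety set |

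In the body of the protocol only one AE test falls under the PP rule. In the synopsis both AE endpoints do. Nothing exempts either.

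**2. Who can be missing from PP but present in the safety set**

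A subject who receives product and leaves before the Week 6 visit is in the FAS and the safety set but not in PP. Section 10.2.1 requires product to be stopped for an AE that contraindicates further dosing, and counts unacceptable worsening of the disease as such an event. A subject who leaves the trial for that reason drops out of PP.

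Two qualifications apply. Section 10.3 asks subjects who stop product early to return for a primary endpoint visit at Week 6. Some of them may therefore remain in PP, and section 14.2 does not settle this. Also, worsening can occur on the active or the vehicle lesion, so the direction of any distortion is unknown.

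**3. How far the FAS repeat covers the gap**

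FAS = all randomised subjects, barring rare justified exclusions.

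Safety set = all treated subjects.

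Difference = randomised subjects who were never treated.

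Section 7.1 puts the first application at the site on Day 1, the day of randomisation, so that difference should be close to nil. The FAS run of the section 14.3.5 test is therefore nearly the safety-set run.

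**4. Whether a within-subject treatment contrast exists**

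For subject i, the signed rank test uses d_i = (events on the delgocitinib lesion) − (events on the vehicle lesion).

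- Lesional or perilesional AE: section 13.3 records target lesion 1 or 2, and section 9.3 maps each lesion to a randomised treatment. d_i exists, whatever the causality.
- Distant or systemic AE: no lesion is recorded and the subject is using both creams. d_i does not exist.
- Subject with an AE: one yes/no value for a person exposed to both treatments. There is no pair to difference.

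Of the three synopsis tests, the related lesion-specific one can be carried out as stated. The other two can be formed only if restricted to lesional or perilesional events.

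**The case against.** The strongest reply is that this is largely a labelling matter. Section 14.3.5 puts a single AE test under PP. Overall AEs and subjects with AEs are handled in section 14.3.9.1 on the safety set. The two sections also describe different analyses, event counts by signed rank and affected lesions by McNemar, so they may use different sets without strict contradiction. The same signed rank test is already planned on the FAS. Section 14.3.11 makes every test descriptive and has the statistical analysis plan finalised on blinded data before the code is broken, while section 14.2 has set decisions documented by then.

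Most of this stands, and it is why the point is small. It does not remove the point: the set called primary for a named safety endpoint is still PP, and the plan does not say which of the two analyses answers that endpoint. Later finalisation is an opportunity to correct the text rather than a correction.

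A second reply also has force. Excluding known wrong-product users has a rationale in a by-treatment lesion comparison, because their lesion labels may not match the cream actually applied. Moving the test to the safety set brings these subjects back, so the change needs an attribution rule.

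**Conclusion.** The point holds and is minor. As written, the primary-labelled AE result can leave out treated subjects who left before Week 6, and the synopsis calls for by-treatment tests that do not exist for distant or systemic AEs. The primary efficacy analysis, power and sample size are not affected. The judgement that harm is small assumes that nearly all randomised subjects receive the Day 1 application and that the FAS and safety-set results are reported alongside PP.

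A reader might infer more than the documents support:

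- **That safety data are lost or an AE signal is hidden.** The FAS repeat and the section 14.3.9.1 analyses cover the treated subjects.
- **That PP favours delgocitinib.** Nothing in the documents fixes a direction.
- **That the planned 20% drop-out measures the loss.** It is an all-cause planning allowance. No rate of leaving for a local AE is given, PP has further exclusions, and some who stop product may stay in PP.
- **That the synopsis tests are impossible altogether.** They can be formed for lesional and perilesional AEs, and section 14.3.9.1 already plans a lesion-level comparison.
- **That the AE window is undefined because collection runs to the safety follow-up visit.** Panel 3 already limits both endpoints to Week 6.

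**What to change.** - In section 14.3.5 and the synopsis, name the safety analysis set for the AE secondary endpoints, and limit the sentences on PP with FAS repeat to the efficacy endpoints.
- In the synopsis, restrict by-treatment testing to lesion-specific AEs, in line with section 14.3.5, and summarise overall AEs and subjects with AEs without a treatment split.
- State how lesion-specific AEs in known wrong-product users are attributed, for example by randomised treatment with a sensitivity analysis that excludes those subjects.

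The cost is a wording change in two places and one added rule, which can be settled while the data are still blinded. No extra data, staff or subjects are needed.
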